3.2 Secondary Objectives

1. To compare the intracellular concentrations of SOF (GS-461203) during pregnancy to available data from nonpregnant women.
2. To compare the protein binding (free fraction) of VEL in pregnant women to available data from nonpregnant women.

3. To determine the rate of sustained viral response (SVR12), defined by undetectable hepatitis C virus twelve weeks after completion of SOF/VEL treatment for 12 weeks during pregnancy.
4. To evaluate the safety for the mother and for the neonate of hepatitis C treatment with SOF/VEL during pregnancy.

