10.2.2 Secondary Endpoints: Maternal

The secondary endpoints of the study are:

- 1) Secondary plasma PK endpoints of VEL, SOF and GS-331007:
 - a. Free-fraction of VEL, SOF and GS-331007
- 2) Secondary PK endpoints for intracellular SOF (GS-461203)
 - a. Pre-dose GS-461203 concentrations from dried blood spots and peripheral blood mononuclear cells
- 3) Maternal sustained virologic response after 12 weeks of therapy (SVR12)
- 4) Adverse events including clinical and laboratory changes
- 5) Pregnancy outcomes including the following:
 - a. delivery prior to 37 completed weeks of gestation
 - b. stillbirth or intrauterine fetal demise
 - c. intrapartum hemorrhage
 - d. postpartum hemorrhage
 - e. non-reassuring fetal status
 - f. chorioamnionitis
 - g. hypertensive disorders of pregnancy
 - h. gestational diabetes
 - i. intrauterine growth restriction

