10.3 Sample Size

To evaluate the primary objective, we estimate a desired sample size of 10 participants. In order to maintain our sample size, any participant who discontinues treatment during the 12-week treatment period will be replaced. Based on SOF/VEL prescribing information, we will have 87% power to detect a 50% decrease in VEL AUC and >99% power to detect a 2-fold increase. For power calculations we chose this degree of change in VEL AUC because the therapeutic range of SOF/VEL is quite wide and decreases in VEL AUC of up to 50% and increases of up to 2-fold are still associated with efficacy and have acceptable safety/tolerability, respectively.

The FDA does not recommend co-administration of VEL with EFV because it decreases the VEL AUC by >50% [34]. Additionally, this sample size provides an estimated power of 0.82 to detect a 25% change in the AUC of the SOF, given the reported interpatient variability of 35.6% among female patients. Power determinations were performed in SAS v. 9.4 (SAS, Cary, NC).

Any participant that discontinues the study before the PK3 visit is completed or if a participant reports missing more than 1 dose per week averaged over the duration of the study then they will be replaced by recruiting another participant into the study.

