10.5.3 Analysis of Safety Endpoints

Rates of abnormal safety laboratory assessments will be compared to those reported in the literature on historic controls and rates of adverse pregnancy outcomes will be compared to historic HCV-infected pregnant women who have delivered at our institution. Statistical significance will be determined by chi-square test.

Qualitative Analysis

Following transcription of the IDIs, the Qual EASE team will develop a qualitative codebook using an editing approach to ensure that all relevant topics and themes are represented. Two trained qualitative coders from Qual EASE will then be trained in the codebook. A primary coder will code all interviews in the pre- and post-treatment interview groups, and a secondary coder will code half of the interviews in the pre- and post-treatment interview groups. Coding will be completed using Atlas.ti software, which will help to determine the frequency and prevalence of the topics and themes which were discussed. Cohen's Kappa scores will be calculated to determine intercoder reliability.

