13.3.2 Benefits

This study is a safety study of use of SOF/VEL in pregnancy and as such the study medication may not treat HCV in pregnancy as it may not be the correct dose. Participants and others may benefit in the future from information learned from this study. Specifically, information learned in this study may lead evidence-based guidance for the treatment of chronic hepatitis C infection in pregnancy and prevention of perinatal HCV transmission.

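### Section 10.5.3 plans only a chi-square significance test, and no interval estimates, for comparing safety rates in about 10 women with historic rates

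*Combined protocol and SAP*

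**What the plan says.** Safety is a stated secondary objective in section 3.2: "To evaluate the safety for the mother and for the neonate of hepatitis C treatment with SOF/VEL during pregnancy". Section 13.3.2 goes further: "This study is a safety study of use of SOF/VEL in pregnancy". Section 10.2.2 lists adverse events, laboratory changes and nine pregnancy outcomes, the first being "delivery prior to 37 completed weeks of gestation".

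Section 10.5.3 gives the analysis in two sentences. For laboratory results, "Rates of abnormal safety laboratory assessments will be compared to those reported in the literature on historic controls". For pregnancy, "rates of adverse pregnancy outcomes will be compared to historic HCV-infected pregnant women who have delivered at our institution". It then adds: "Statistical significance will be determined by chi-square test".

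No significance level, sidedness, historic rate, historic sample size, interval estimate or multiplicity rule is given for these comparisons. Section 10.5.1, by contrast, plans geometric mean ratios with 90% confidence intervals for the pharmacokinetic parameters.

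On size, section 10.3 says "we estimate a desired sample size of 10 participants" and supports this with power for VEL and SOF exposure only. It also says "any participant who discontinues treatment during the 12-week treatment period will be replaced". Section 10.5.3 does not say whether a replaced woman stays in the safety denominator.

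**The concern.** When a significance test is the only inferential method, the reported result for each outcome is whether p falls below a threshold. With 10 women that depends on one or two events. A non-significant result fits both no excess and a large excess. A significant result on a rare laboratory abnormality can rest on a single woman.

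Section 2.5 places this trial before larger treatment studies, so its safety tables will be read by people planning those studies. They need to know which rates of preterm delivery, growth restriction or laboratory abnormality the data leave open. The planned output does not tell them, although the plan already uses intervals for the pharmacokinetic results.

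**Working it through.** The plan gives no power or error rate for the safety comparisons, so there is no figure to reproduce.

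**Inputs from the documents**
- Treated women: 10 (section 10.3).
- Test: chi-square, with no correction or exact method named (section 10.5.3).
- Rates on SOF/VEL in section 2.4.1: lipase elevation 3%, 6% and 3%; creatine kinase elevation 1%, 2% and 1%.

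**Assumptions, because the plan is silent**
- Two-sided 5% level, counting rejections in the direction of harm.
- Historic rate p0 of 3%, 5%, 10%, 15% or 20%, plus 1% for the rarest laboratory event.
- Historic sample m of 100, 369 or 1000. The 369 is the size of the institutional cohort in section 2.2. That cohort is cited for referral and treatment and is not named as the safety comparator, so it only illustrates scale.
- Effect of interest: a doubling.

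**Step 1. The test.** With x events in 10 and y in m, the pooled rate is p = (x + y)/(10 + m), and

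z = (x/10 − y/m) / √[p(1 − p)(1/10 + 1/m)].

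An excess is flagged when z > 1.96.

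Example with a historic rate near 10% (37 of 369):
- 2 of 10: p = 39/379 = 0.103, z = 0.0997/0.0974 = 1.02, two-sided p-value 0.31.
- 3 of 10: p = 40/379 = 0.106, z = 0.1997/0.0985 = 2.03, p-value 0.04.

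One woman separates the two verdicts.

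**Step 2. Chance of detecting a doubling.** Power is the sum, over every (x, y) with z > 1.96, of Bin(x; 10, 2p0) × Bin(y; m, p0). Exact enumeration gives:

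| True change | m = 100 | m = 369 | m = 1000 |
|---|---|---|---|
| 3% to 6% | 16.6% | 12.8% | 12.0% |
| 5% to 10% | 16.7% | 18.9% | 22.3% |
| 10% to 20% | 21.5% | 24.5% | 27.3% |
| 15% to 30% | 27.7% | 30.7% | 33.6% |
| 20% to 40% | 34.6% | 36.4% | 36.7% |

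Power runs from 12.0% to 36.7%, so a doubling is missed 63.3% to 88.0% of the time. At a 1% historic rate, 82% to 86% of doublings are missed, which is inside the same range.

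**Step 3. False alarms on rare events.** Take a 1% historic rate and no true excess. A single event in 10 against 10 of 1000 gives p = 11/1010 = 0.0109 and z = 0.090/0.0330 = 2.73, which is significant. The chance of at least one event in 10 is 1 − 0.99^10 = 9.6%. Allowing for variation in the historic count, enumeration gives false flags of 7.2% (m = 100), 8.0% (m = 369) and 9.4% (m = 1000), against a nominal upper-tail 2.5%.

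**Step 4. An exact test alone does not help.** Fisher's test against 100 or 369 historic women has power of about 8% to 9% for 5% to 10%, 15% for 10% to 20%, and 28% to 33% for 20% to 40%. It would still miss about 67% to 92% of these doublings.

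**Step 5. What 10 women can show.** Exact (Clopper-Pearson) 95% intervals:
- 0 of 10: 0 to 30.8%, the upper limit being 1 − 0.025^(1/10)
- 1 of 10: 0.3% to 44.5%
- 2 of 10: 2.5% to 55.6%
- 3 of 10: 6.7% to 65.2%

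The 2-of-10 result in Step 1 would appear under the present plan as non-significant. The interval shows that rates from 2.5% to 55.6% remain compatible with it.

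**The case against.** The strongest reply is that this is a small pharmacokinetic pilot. Safety is secondary, nobody expects power for it, and safety is not left to a p-value. Two independent physicians review safety data monthly (sections 8.1, 8.2 and 10.5.4), a pause or stop can be recommended (section 8.2), and individual discontinuation criteria are set out in sections 9.3 and 9.4. All of this stands. Lack of safety power is not itself a fault, and the test is the only inferential method in section 10.5.3, not the only safety judgement in the trial. But those provisions govern conduct and participant protection. They do not say how the final rates are to be estimated or reported.

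A reader might infer that the plan treats non-significance as evidence of safety. The text does not say so: section 10.5.3 has no rule for a non-significant result, and no later decision is tied to one. Section 13.3.1 openly states that fetal effects are unknown. The misreading is a risk that the plan does not guard against; it is not something the plan asserts.

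A reader might also infer that almost any result in 10 women would be non-significant. That is too strong. Under the same assumptions a tripling from 15% to 45% is detected 64% to 72% of the time, and one from 20% to 60% is detected 79% to 83% of the time. A tripling from 10% to 30%, however, is still missed 45% to 53% of the time.

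Finally, every percentage here depends on an assumed level, baseline, historic sample and effect size. That is true, and is why ranges are shown.

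**Conclusion.** The point holds as a weakness in the analysis method. Section 10.5.3 rests its safety comparisons on a test that, with about 10 women, misses a doubling roughly 63% to 88% of the time and over-flags at the lowest laboratory rate roughly 7% to 9% of the time. It plans no interval that would show this uncertainty. Nine pregnancy outcomes plus the laboratory tests, with no multiplicity rule, add to the chance of a spurious flag.

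The figures assume a two-sided 5% level, an uncorrected chi-square test and 100 to 1000 historic women. The miss rate assumes historic rates of 3% to 20%; the false-flag rate assumes 1%. The need for intervals depends on none of these choices, because 0 of 10 leaves rates up to 30.8% open whatever the comparator.

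The documents do not support the conclusion that the plan declares the drug safe when p exceeds 0.05, or that safety oversight is absent. The primary pharmacokinetic analysis is unaffected.

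**What to change.** Replace the significance sentence in section 10.5.3 with:

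> For each safety laboratory abnormality and each pregnancy outcome, the number and percentage of women affected will be reported among all women who took study drug, including any who were replaced, with the exact (Clopper-Pearson) 95% confidence interval, next to the historic rate and its source. Any p-values are descriptive. A non-significant difference will not be interpreted as evidence of safety; for example, 0 of 10 has an upper 95% limit of 30.8%.

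The denominator wording matters because replaced women will usually have taken study drug. Section 5.1.2 expects no more than one replacement. With 11 women and no events, the upper limit would be 1 − 0.025^(1/11) = 28.5%, so the limit should be computed from the actual number treated.

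The cost is one paragraph and a few extra table columns, with no added women, visits or samples. The downside is a less favourable safety statement, because the intervals will be wide.

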10.5.4 Data and Safety Monitoring Plan

No Data and Safety Monitoring Board oversight is planned for this study, however a Study Steering Committee comprised by the Protocol Chair, a second physician

investigator from the University of Pittsburgh, a laboratory scientist from the University of Pittsburgh, the Data Management lead statistician and a representative from Gilead Sciences Clinical Research will provide oversight. Reviews of study progress, including rates of participant accrual, retention, completion of primary and main secondary endpoint assessments will take place approximately every 3 months, and as needed. At the time of these reviews, or at any other time, the Study Steering Committee may recommend that the study proceed as designed, proceed with design modifications, or be discontinued. Two independent safety physicians experienced with monitoring of clinical trials among pregnant women will conduct interim safety reviews on a monthly basis or more frequently at the request of the Study Steering Committee.

11 DATA HANDLING AND RECORDKEEPING

11.1 Data Management Responsibilities

Study questionnaires will be developed by the study team in conjunction with data management.

11.2 Source Documents and Access to Source Data/Documents

The site will maintain source data/documents in accordance with current DAIDS policies. (<http://rsc.tech-res.com/policiesandregulations/>)

The study team will maintain, and store securely, complete, accurate and current study records throughout the study. In accordance with U.S. regulations regarding testing investigational medications, the study investigator will maintain all study documentation for at least two years following the date of marketing approval for the study medications being tested for the indication in which they were studied. If no marketing application is filed, or if the application is not approved, the records will be retained for two years after the investigation is discontinued and the US FDA is notified. For research involving children, records shall be retained at least until the pediatric subject reaches the age of 23.

Study records will be maintained on site for the entire period of study implementation.

11.3 Quality Control and Quality Assurance

The study site will conduct quality control and quality assurance procedures in accordance with site SOPs.

12 CLINICAL SITE MONITORING

As this is an investigator initiated IND study, monitoring will be performed by internal clinical study staff (i.e. QA/QC Reviewer), PoR, laboratory staff and local data management team. Internal reviews will include:

- Review informed consent forms, protocol procedures, and study documentation
- Assess compliance with the study protocol, Good Clinical Practices (GCP) guidelines, and applicable regulatory requirements (US and non-US), including CFR Title 45 Part 46 and Title 21 Parts 50, 56, and 312
- Perform source document verification to ensure the accuracy and completeness of study data
- Verify proper collection and storage of biological specimens
- Verify proper storage, dispensing, and accountability of investigational study medications

The Education and Compliance Support for Human Subject Research (ECS-HSR), Office of Research Protections will also oversee study activities. The ECS-HSR has extensive experience in the auditing and monitoring of clinical investigations for compliance with GCP standards and IND commitments. To ensure appropriate institutional oversight of University-based IND applications, the ECS-HSR will periodically monitor the research oversight programs of IND Sponsors, which will include compliance of the Sponsor and Investigator with applicable FDA regulations, applicable University of Pittsburgh policies and the IRB-approved protocol and consent document. The frequency of these monitoring visits shall be determined by the ECS-HSR.

The study investigators also will allow inspection of all study-related documentation by authorized representatives of Gilead Sciences, FDA, OHRP, IRBs/ECs and other local and US regulatory authorities.

13 HUMAN SUBJECTS PROTECTIONS

Study investigators will make efforts to minimize risks to participants. Informed consent will be reviewed in detail with potential participants and all questions will be adequately answered prior to obtaining written informed consent. All eligibility criteria will be verified prior to initiation of investigational product. Recruitment will begin after receiving IRB approval and after the protocol has been submitted to the FDA. The study investigators will permit audits by the NIH, Gilead Sciences, the FDA, OHRP, IRB, and other local and US regulatory authorities or any of their appointed agents.

13.1 Institutional Review Boards

The study staff will ensure that the protocol, associated informed consent form, and study-related documents (such as participant education and recruitment materials) are reviewed and approved by the University of Pittsburgh IRB prior to starting the study. Any amendments to the protocol or informed consent will be approved by the University of Pittsburgh IRB prior to implementation.

13.2 Study Coordination

[name] MSc holds the Investigational New Drug (IND) application for this study. Assignment of all sponsor responsibilities for this study will be specified in a Clinical Trials Agreement (CTA) executed by the University of Pittsburgh and Gilead Sciences. [name] will work closely with The University of Pittsburgh Office for Investigator-Sponsored IND and IDE Support (O3IS) who provides assistance to University researchers in order to ensure IND submission and notification requirements are met.

Close coordination between the study team is necessary to track recruitment, enrollment, retention, AEs and unanticipated problems and to address other issues that may arise in a timely manner. The study investigators and the independent safety physician will address issues related to study eligibility, AE management/reporting and unanticipated problems as needed to assure consistency. Rates of accrual, protocol adherence, retention, and AE incidence will be reported by data management and monitored closely by the team as well as the Study Steering Committee.

13.3 Risk Benefit Statement

13.3.1 Risks

General/Maternal

As with any research study, there may be adverse events or side effects for the maternal participant or the fetus/infant that are currently unknown and certain of these unknown risks could be permanent, severe or life-threatening.

There are no studies of SOF/VEL in pregnant women. However there has been one study of a similar medication ledipasvir/sofosbuvir in 9 pregnant women. There were no adverse events greater than grade 2 that were related ledipasvir/sofosbuvir. There have been animal studies done in rats and rabbits as detailed in section 2.4.2. No effects on fetal development have been observed in rats and rabbits at the highest doses tested. However, animal reproductive studies are not always predictive of human response.

It is also not known if SOF/VEL is present in human breast milk. If the participant delivers while still on study medication and intends to breast feed, study medication will be discontinued and HCV resistance testing will be done at the next study visit.

There is a potential risk that the hepatitis virus may become resistant to SOF/VEL because the dose may not be adequate for treating pregnant women with hepatitis C or if the participant does not complete the entire 12 weeks of study medication. If resistance occurs, this may limit the choices of effective therapy after pregnancy for the participant and/or possibly her infant.

Overall, SOF/VEL was well tolerated by patients with chronic HCV infection (N=1035) with only 2 participants permanently discontinued treatment due to adverse events (0.2%). The most common adverse reactions (adverse events assessed as causally related by the investigator and at least 10%) were headache and fatigue. Adverse reactions, all grades, observed in greater than or equal to 5% of participants receiving 12 weeks of treatment with SOF/VEL in ASTRAL-1 include: headache (22%), fatigue (15%), nausea (9%), asthenia (5%), and insomnia (5%). Of subjects receiving SOF/VEL, 79% had an adverse reaction of mild severity (Grade 1). With the exception of asthenia, each of these adverse reactions occurred at a similar frequency or more frequently in participants treated with placebo compared to participants treated with SOF/VEL (asthenia: 3% versus 5% for the placebo and SOF/VEL groups, respectively). The adverse reactions observed in participants treated with SOF/VEL in ASTRAL-2 and ASTRAL-3 were consistent with those observed in ASTRAL-1. Irritability was also observed in greater than or equal to 5% of participants treated with SOF/VEL in ASTRAL-3. In the ASTRAL-1 study, rash occurred in 2% of participants treated with SOF/VEL and in 1% of participants taking placebo. No serious adverse reactions of rash occurred and all rashes were mild or moderate in severity. In the ASTRAL-1 study, depressed mood occurred in 1% of participants treated with SOF/VEL and was not reported by any placebo participants. No serious adverse reactions of depressed mood occurred and all events were mild or moderate in severity.

Hepatitis B virus (HBV) reactivation has been reported in HCV/HBV coinfect ed patients who were undergoing or had completed treatment with HCV direct acting antivirals, and who were not receiving HBV antiviral therapy. Some cases have resulted in fulminant hepatitis, hepatic failure, and death. Cases have been reported in patients who are HBsAg positive and also in patients with serologic evidence of resolved HBV infection (i.e., HBsAg negative and anti-HBc positive). We will exclude participants that are anti-HBc positive for this reason. Additionally, postmarketing cases of symptomatic bradycardia and cases requiring pacemaker intervention have been reported when amiodarone is coadministered with a sofosbuvir-containing regimen. Additionally, a fatal cardiac arrest occurred in a patient taking amiodarone that was co-administered with sofosbuvir. For this reason, we will exclude participants who are taking amiodarone.

Laboratory abnormalities:

Lipase Elevations: In ASTRAL-1, isolated, asymptomatic lipase elevations of greater than 3 times the upper limit of normal were observed in 3% and 1% of participants treated with SOF/VEL and placebo for 12 weeks, respectively; and in 6% and 3% of participants treated with SOF/VEL in ASTRAL-2 and ASTRAL-3, respectively.

Creatine Kinase: In ASTRAL-1, isolated, asymptomatic creatine kinase elevations greater than or equal to 10 times the upper limit of normal were reported in 1% and 0% of participants treated with SOF/VEL and placebo for 12 weeks, respectively; and in 2% and 1% of participants treated with SOF/VEL in ASTRAL-2 and ASTRAL-3, respectively.

There are known drug interactions with SOF/VEL and other prescription and non-prescription medications. A comprehensive list of medications will be obtained from participants including over-the-counter medications (i.e. antacids, St. John's wort) and compared to the package insert to assess any contraindication to participation or necessary alterations in dosing schedules with use of the study medication.

Phlebotomy or starting an IV may lead to excessive bleeding, discomfort, feelings of dizziness or faintness, and/or bruising, swelling and/or infection.

Disclosure of HIV status may cause worry, sadness or depression. Disclosure of HIV-positive status has been associated with depression, suicidal ideation, and denial as well as social isolation. Trained counselors will be available to help participants deal with these feelings.

Participation in clinical research includes the risk of confidentiality loss.

Participants will be asked to provide personal/protected health information (PHI). All attempts will be made to keep PHI confidential within the limits of the law. However, there is a chance that unauthorized persons will see PHI. All paper records will be kept in a locked file cabinet or maintained in a locked room at Magee. Electronic files will be password protected. Only people who are involved in the conduct, oversight, monitoring, or auditing of this study will be allowed access to the PHI that is collected. Any publications from this study will not use information that will identify participants by name. Organizations that may inspect and/or copy research records maintained at the participating sites for quality assurance and data analysis include groups such as the study sponsor, the National Institute of Health (NIH) or its designee and the US Food and Drug Administration (FDA).

Technology assisted-directly observed therapy: There is a risk that people outside of the research team will see the directly observed dosing. The photo/video recording

of the dosing will be taken directly into the PittBox app and stored in this system for the research staff to access. . While the app is password protected, someone may access the information if they gain access to the password/app on the participant's personal device. Likewise, the telephone numbers for these communications could also be visible to third parties.

Fetus/infant:

There is not data on use of this medication during pregnancy so the effects on a fetus/unborn child are not known. The study medication may cross the placenta and get to the fetus/unborn infant exposing the fetus to the study medication. It is unknown whether a fetus/unborn infant whose mother took SOF/VEL during pregnancy will develop normally or have side effects.

Obtaining blood samples from the infant may cause them to cry, cause bleeding, bruising or a clot and may be distressful to watch the infant have their blood drawn.

